3.3 Preclinical Evidence

Several *in vitro* experiments have shown that nasal chondrocytes are a suitable cell source for the production of tissue engineered cartilage grafts to treat articular cartilage injuries in the knee. This is not only due to their advantageous properties as compared to articular chondrocytes, but also due to the facts that nasal chondrocytes can adapt to the environment of the knee regarding weight loading and their resistance to inflammatory responses (see chapter 3.2).

Furthermore several animal studies have been performed to investigate the behavior of tissue engineered nasal cartilage in the environment of the joint.

\/	ment:
Version: V07	on:
Page number: 35 of 80	number:
Acronym Nose to Knee II	ıym

Migration study (see IB for details)

To answer the question whether implanted nasal chondrocytes are still detectable in the repair tissue and/or migrating in surrounding articular tissues, we performed two experiments in a goat animal model where autologous articular chondrocytes, labelled using GFP lentivirus for tracking purposes, were cultured in Chondro-Gide® and implanted in a joint defect.

After 4 weeks, 3 months and 6 months respectively, animals were sacrificed and immunohistochemical analysis of reparative tissue showed that GFP positive chondrocytes were still detected in the tissue, indicating that the implanted chondrocytes remained at the site of implantation. In addition, the reparative tissue was cartilaginous, as demonstrated by positive Safranin-O staining specific for cartilage extracellular matrix. After 3 months chondrocytes were exhibiting typical shape within lacuna but were not displaying a columnar organization.

No GPF-positive chondrocytes could be detected by FACS analyses in any of the tissues surrounding the joint/implantation site (fat pad, patella, meniscus, cruciate ligaments, and synovium; n = 3 goats). Therefore, it could be concluded that the implanted chondrocytes, either from articular or from nasal origin, did not migrate into the tissues surrounding the joint up to 3 months after implantation (Mumme et al, 2016).

Tumorigenicity (see IB for details)

Different groups have reported that chondrocytes from different cell sources showed no signs of malignant transformation after cell expansion in 2D, assessed by different techniques (Kamil et al, 2002 and 2003, Brandl et al, 2010, Trimborn et al, 2011).

The N-TEC, composed of autologous nasal chondrocytes and the Chondro-Gide® membrane, has been used in a previous clinical trial "Tissue engineered nasal cartilage for reconstruction of the alar lobule" (TpP-I-2010-002) for reconstructive purposes following resection of a non-melanoma skin cancer and thus implanted in a tumor site. Second look biopsies were analyzed 6 months after implantation and histological analysis performed by a pathologist. There was no evidence of tumor formation. The one year follow-up also showed no indication of tumor formation in any of the patients.

The same nasal cartilage graft was used in a second clinical trial "Tissue engineered nasal cartilage for the regeneration of articular cartilage in the knee after traumatic injury- phase I clinical trial" (TpP-I-2012-001). There was no indication of local tumor formation detected in the MRI of the 1 or 2 year follow-up for the first patients.

In addition an animal study (mouse) was performed to assess the tumor potential of constructs generated with nasal chondrocytes from 3 patients of the previous trial expanded in 2D in the presence of growth factors. After implantation none of the operated mice showed weight loss or abnormalities with palpation indicating absence of tumor at the implantation site. After 6 months constructs were explanted and assessed histologically. In addition, five different organs (lung, liver, the kidneys, spleen, and local lymph nodes) were harvested from the same mice, No signs of tumor formation could be found in any of the explanted tissues, Therefore it can be concluded that the expanded nasal chondrocytes do not have any tumor potential when used for cell based constructs.

Capacity for cartilage repair (see IB for details)

A long-term study in goats was performed to obtain preclinical evidence of the suitability of NC for the repair of articular cartilage defects. Tissue-engineered constructs were generated using autologous NC (and AC to serve as controls) and implanted into experimental defects created at a clinically relevant location, namely load-bearing sites of the articular condyle. The results of this study (Pelttari et al., 2014) show, per the semi quantitative O'Driscoll scoring system, that the quality of the repair tissue significantly improved from 3 to 6 months after implantation only when using NCs, such that at 6 months the repair quality achieved by NCs was statistically superior to AC controls. The improved quality of the repair tissue using NC compared with AC was confirmed histologically by a stronger and more uniform staining for glycosaminoglycans at 6 months (figure 3.3.1).

Document:	Clinical Study Protocol
Version:	V07
Page number:	36 of 80
Acronym	Nose to Knee II

A 25 20-	*	*	3 months 6 months
O'Driscoll Score	T	T Ac	
В	NC		AC
			Mass of
11/4	d n	n	d
			000 90 ga

Fig. 3.3.1 Goat nasal chondrocytes (NC) in articular cartilage repair. (**A**) O'Driscoll scores of the repair quality of the NC- or AC-treated goat articular defects at 3 and 6 months (n = 3 animals per time point) after implantation. * = p<0.05. (**B**) Safranin O and Alcian blue staining of representative repair tissues at the defect site (d) and of adjacent native articular cartilage (n) 6 months after implantation of NC or AC. Lower Alcian blue images show higher magnification (scale bar, $50 \, \text{m}$) of the regions framed in the respective upper panels (scale bar, $1 \, \text{mm}$)

In summary, the results of these animal studies support the compatibility and efficacy of nasal chondrocytes for articular cartilage repair.

??? ? ?		[२।२।४१।२। तर्षाः । तर्षः । तर्षः । तर्षः । तर्षः । तर्षः ।
37 7? ???		१२।३।४१।३।४१।३।४१।३।४१।३।४१।३।४१।३।४१।३।
?????????????	??क्किकि	

Table 3.4.3: Improvement of clinical scores: Average and individual basis

The radiological evaluation of N-TEC treatment is promising (figure 3.4.2). The quantification of glycosaminoglycan by dGEMRIC indicates hyaline cartilage tissue formation. More precisely, by comparison of the repair tissue with native healthy cartilage from radiological measurements, the relative \Box R1 has been calculated (1.0 indicating no difference detectable between repair tissue and native healthy cartilage). With the resulting relative \Box R1 of 1.9 (0.89 – 4.13) after 6 months, 1.5 (0.78 – 2.17) after 12 months and 1.20 (0.71 - 1.51) after 24 months, a progressive additional maturation of the tissue over time can be observed. This is further supported by histological data (figure 3.4.3). When compared to literature, N-TEC treatment might result in even more hyaline tissue compared to MACI (relative \Box R1 2.18, Trattnig et al 2008) or ACT (2.40, Trattnig et al 2007) or microfracture (3.39, Trattnig et al 2008). The morphological MOCART score after 6 months was 61 (25-80), after 12 months 56 (25-80) and after 24 months 48 (10-80). This might be due to occasional cleft formation at the interface between native and repair cartilage.

Document:	Clinical Study Protocol
Version:	V07
Page number:	40 of 80
Acronym	Nose to Knee II

A	В	c (

Fig. 3.4.2 Sagittal MRI of the knee before surgery (A) indicating the cartilage defect (red circle). Maturation of the repair tissue after 6 months (B) and 12 months (C), demonstrating the repair tissue in situ.

[figure not shown]

Fig. 3.4.3 Histological analysis indicates chondrogenic differentiation of the graft at time of implantation (A). 18 months after surgery, the repair tissue is more mature with abundant deposition of glycosaminoglycans (B) and with positive collagen type II (C) and widely negative collagen type I immunohistochemistry (D) typical for hyaline cartilage.

Clinical trial Phase II: Nose to Knee II (2016TpP2004, EudraCT: 2015-005162-34)

The current clinical trial "Nose to Knee II" described in this study protocol is a phase II multicenter clinical trial based on the phase I study described above, which focuses on efficacy and the comparison of grafts in different maturation stages and therefore requires higher patient numbers to be statistically significant. Patients, between 18 and 65 years old, suffering from articular cartilage lesions not related to an inflammatory state, are treated in four different countries: Croatia, Germany, Italy and Switzerland and will be followed up for 2 years. At 6 weeks as well as 3, 12 and 24 months after the operation, follow-ups are performed. During the follow-ups at 12 and 24 months questionnaires (KOOS, EQ-5d) are filled out by the patient and MRIs will be performed at 3,12 and 24 months.

3.6 Explanation for choice of comparator (or placebo)

As the most promising approach currently, and reported to provide clinical improvement to young patients with focal cartilage defects in mid-term follow-up (Kon et al, 2009), we have selected cell-therapy techniques as the most appropriate comparator. The established cell-based technique MACI® has been used in clinical applications since 1998 and is a standard product with marketing authorization in Europe since 2013 (currently suspended). In order to eliminate differences due to the cell source and allow a more appropriate evaluation of the impact of graft maturation on the clinical outcome, nasal chondrocytes instead of articular chondrocytes will be used (figure. 3.6.1), therefore exploiting the concept of cellular therapies, not using a licensed product. Since nasal chondrocytes have been proven *in vitro* to have superior properties as compared to articular chondrocytes, results at least comparable to the standard MACI® procedure can be expected.

[figure not shown]

Fig. 3.6.1 Illustration of the procedures to generate the NC-based IMPs and of their main characteristics

Document:	Clinical Study Protocol
Version:	V07
Page number:	42 of 80
Acronym	Nose to Knee II

We believe that in this setting, where a mature and immature graft is manufactured in a similar way using nasal chondrocytes, the superiority of the mature graft in comparison to the immature graft can be shown.

3.7 Risks / Benefits

The spontaneous healing capacity of cartilage is poor and untreated defects predispose to osteoarthritis. Common current strategies such as arthroscopic debridement, microfracture, autologous osteochondral grafting, cartilage allografts and autologous chondrocytes implantation (ACI/MACI) still have drawbacks or produce unsatisfactory long term results. These drawbacks could be overcome using a tissue based therapy.

Potential risks and benefits

During this trial all patients will be treated according to current hospital standards. Nasal cartilage biopsies will be harvested by an experienced plastic or ENT-surgeon. The manufacturing of the graft will be performed in a GMP-facility with given manufacturing authorization from Regierung von Oberfranken, Ansbach, Germany in consultation with PEI (NCA) or from Swissmedic, Switzerland depending on the manufacturing site. Manufacturing will be performed in compliance with GMPguidelines and according to verified protocols. In-Process controls will be conducted at defined points during the process to ensure absence of microbiological, endotoxin or mycoplasma contamination. The quality of the graft will be tested before implantation according to verified protocols. Experienced orthopedic surgeons will implant the graft into the knee and perform the follow-up. Technically the operation is no more challenging than standard procedures as ACI, and the follow-up includes all standard procedures with the addition of an MRI analysis. Since autologous cells are implanted and autologous serum is used instead of bovine serum, the risk of immune reaction or of disease transmission is minimal. Furthermore, in vitro and in vivo studies have already proven that nasal chondrocytes can survive in the joint environment and respond to mechanical loading similar to articular chondrocytes. The certified Chondro-Gide® membrane is already in clinical use. The combination of nasal chondrocytes cultured in this matrix has already successfully been used in two other clinical trials, for the reconstruction of the alar lobule after tumor resection and for the treatment of cartilage defects in the knee.

From standard therapies it is known that localized defects on the patella on average have higher complication rates and clinically inferior outcomes as compared to defects on the femoral condyle or trochlea. For N-CAM and N-TEC treatment, there are no clinical data available yet concerning the outcome of treatment for patella defects.

Taking into account the pre-clinical results and safety measures, the risk for the patient is not increased as compared to the standard procedures.

However, several benefits can be expected from the implantation of cartilage grafts into focal cartilage defects as compared to state-of-the-art surgical treatments:

1. Shorter rehabilitation times

Implantation of a more mature tissue should lead to shorter rehabilitation times, earlier postoperative joint loading and a faster return of the patient to daily life activities and sports.

2. Possibility to treat larger defects

This technique can be used for cartilage defects up to 8 cm² in size.

3. More durable regeneration

We assume that in the long term the repair tissue will be hyaline cartilage instead of fibrocartilage and will therefore have better durability and stability as compared to the outcome of current methods.

4. Reduced donor-site morbidity

When AC are used for cartilage repair currently, harvesting of autologous cartilage plugs or biopsies from a low weight bearing site generate an additional defect in the joint, which has been reported to be detrimental to the surrounding healthy articular cartilage. Biopsies taken from the nasal septum lead to negligible donor-site morbidity. Safety of harvesting procedure was previously reported in a first trial in which similar nasal cartilage biopsies were taken to generate tissue engineered grafts for the reconstruction of alar lobule after tumor resection (Clinicaltrials.gov: NCT01242618, Fulco et al, Lancet 2014).

5. Superior graft quality

Articular cartilage has to be harvested from a healthy, low weight bearing area, therefore limiting the Study Protocol Nose to Knee II, April 10, 2018, Version 07 Page 42 of 80

Document:	Clinical Study Protocol
Version:	V07
Page number:	43 of 80
Acronym	Nose to Knee II

availability of material. In case of some diseases harvesting of healthy cartilage might not even be possible. Furthermore, it has been shown that properties of articular chondrocytes are dependent on age, while those of nasal chondrocytes are less age dependent and show greater proliferation and differentiation capacity. This might allow this technique to be applied to older patients or those with insufficient amounts of healthy articular cartilage.

Overall the risk for the patient is not considered to be higher as compared to standard procedures, but the benefits might have a significant impact especially for large defects.

Expected Adverse Reactions

Based on the experience of the phase I study, no major risks are expected. Expected adverse reactions are mostly related to the tissue withdrawal and implantation:

Expected Adverse Reaction related to nose cartilage withdrawal

		hematoma
ш	LUCAI	Helliatollia

- Local bleeding
- Local pain

Expected Adverse Reaction related to tissue implantation

Local:

- Pain
- Swelling and/or hematoma
- Plate removal in case of necessary osteotomy

Systemic:

- Post-anesthetic nausea
- vomiting
- fever

No adverse reactions are expected to follow-up procedures such as MRI/dGEMRIC. These expected adverse reactions are common for the standard treatment and therefore will only be classified according to chapter 10.1.1 and recorded in the CRF. They are not subject to reporting.

Risk assessment

Risks could be related to the manufacturing, the quality of the product itself or the implantation of the product. Due to the use of a certified, clinically used matrix with autologous cells, the adherence to GMP- and GCP-regulation and a close follow-up schedule, the overall risk for the patient is expected to be low. Possible risks have been identified, evaluated and appropriate measures to reduce the risk described (Table 3.7.1). For residual risk a contingency plan is available. If, during the process, further risks are identified or other measures have to be taken, the plan will be adapted. Microbiological, Endotoxin and Mycoplasma testing will be carried out as in process controls. In case of serious adverse events related to the IMP, the respective ethical commissions and national authorities will be informed. Along with the patient information, the patient receives the contact details of the responsible doctor along with the instruction to contact the doctor at any time for any ambiguities, emergencies, unexpected or adverse events during or after the study.

In summary, this procedure contains no expected additional risks as compared to the standard procedure for these cases.

Major	High chance of occurrence, critical for the trial
Medium	Medium chance of occurrence, critical for the trial
Minor	Low chance of occurrence, may be critical for the trial
Acceptable	No contingency plan required

Document:	Clinical Study Protocol
Version:	V07
Page number:	44 of 80
Acronym	Nose to Knee II

Table 3.7.1: Risk factors in the use of a tissue engineered products for cartilage regeneration.

Risk		Initial risk	Risk Control/Mitigation	Residual Risk	Contingency Plan
	Contamination of biopsy	medium	 Biopsy harvesting according to Good Clinical Practice Check for microbiological contamination in the supernatant of the biopsy after transport Training of plastic surgeons Addition of antibiotics in the transport medium and first week of expansion 		
Construct	Contamination during media change	medium	 Check for microbiological & endotoxin contamination and mycoplasma in the media after expansion and pre-culture phase Use of clean room Work according to SOPs 	minor	abort of the transplant generation if there are positive results for contamination
	Contamination during transport	minor	Packaging according to the norm for sterile packingWork according to SOP	acceptable	
	Failure to generate a graft	medium	if the standard surgical method has to be used, there is no disadvantage	acceptable	
	Cell number for seeding not reached	medium	 working according to SOPs correct biopsy size 	minor	In case of <50M and >38M cells, ≥95% viability and adequate morphology seeding of a smaller scaffold
	contamination with	the construct is a critical risk. Since most cultures show signs in 48h, the sample of the last media change is taken 48 - 72h prior ast result will be retrospective regarding microbiological contamination.		18 - 72h prior to	
Risk		Initial risk	Risk Control/Mitigation	Residual Risk	Contingency Plan
itient	Infection during surgical intervention at the biopsy site	minor	 standard preparation of patient for operation additional treatment of the biopsy site to avoid infection routine precautions as in any operation 	acceptable	
Safety for patient	Infection through transplant	minor	no positive tests regarding mycoplasma, endotoxin or microbiological contamination (last result retrospective)	acceptable	
	Infection after operation	minor	same as for standard operation	acceptable	

Document:	Clinical Study Protocol
Version:	V07
Page number:	45 of 80
Acronym	Nose to Knee II

			close follow up of patient		
	Complications after implantation	minor	 same as for standard operation arthroscopy to determine cause and further treatment 	acceptable	
	Loss of implant	minor	same as for standard operation	acceptable	
	Rejections and immune reaction	minor	autologous cells and serum are used	acceptable	
	Contrast agent (Dotarem®)associ ated with nephrogenic systemic fibrosis	minor	exclusion of patients with renal impairment	acceptable	
	Allergic or hypersensitive reactions to contrast agent (Dotarem®)	minor	 patients with known allergies or asthma will receive anti-allergy medication before operation 	acceptable	
	Allergic reaction to antibiotics used partially during production	minor	exclusion of patients with known allergies	acceptable	
	Unforeseen side effects	minor	 immediate contact with study doctor for further investigation and treatment 	acceptable	
Risk		Initial risk	Risk Control/Mitigation	Residual Risk	Contingency Plan
	Insufficient patient information	minor	no participation of patient without signed informed consents	acceptable	
Patient's rights	Protection of personal rights	minor	 no personal data besides those relevant for the study (age and sex) given to people involved in the production data treated according to usual hospital practice 	acceptable	
	Incidental findings during screening or follow-up	medium	 patient will be asked as part of informed consent whether he/she would like to be informed of these 	acceptable	

Document:	Clinical Study Protocol
Version:	V07
Page number:	46 of 80
Acronym	Nose to Knee II

Potential threats to the study

Beyond our studies, no engineered cartilage has been used in patients for cartilage regeneration. Even though several products have been claimed as engineered cartilage implants, histological analyses have shown limited matrix deposition. (figure 3.7.1).

[figure not shown]

Fig. 3.7.1 Histological images of the four different scaffolds types. Cell morphology and matrix deposition are shown in histological alcian blue stainings (A, C, D), hematoxylin and eosin staining (B), or in Safranin-O staining (E). Note the presence of chondrocytes but no matrix deposited. (A-D) From Albrecht C et al, 2011.

Post-trial care

Patients will be followed-up on a voluntary basis up to 5 years after implantation and can contact study doctors at any time during or after the study.

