9.2.5 Assessment of safety outcomes

9.2.5.1 Adverse events

All AEs (see Chapter 10 for definition) will be recorded in the eCRF. Among the expected adverse events are those associated with the application of the IMP (anesthesia & operation) as described in Chapter 3.7 under "Risks & Benefits". Other adverse events can be associated with surgical and medical procedures, arthralgia, joint effusion, decreased joint range of motion, and infections (joint, wound) or related to the IMP itself. These parameters will be checked at each follow-up visit or if the patient reports any kind of indisposition in between the visits.

All SAEs will be reported to the Sponsor-investigator or his designee according to the SOP of the Sponsor. Information in the reporting form includes: reporting center, Patient-ID, Information on surgery, other treatments already performed and details of the adverse event (affected site, symptoms, time of onset/end, time course, diagnosis and expected outcome (if possible)). The PI of the respective clinic as well as the Sponsor-investigator or his designee will perform an assessment on causality and decide on the necessary reporting.

All SAEs resulting in death will be reported to the ethical committee and the national competent authority as well as to Swissmedic within 7 days.

Document:	Clinical Study Protocol
Version:	V07
Page number:	58 of 80
Acronym	Nose to Knee II

All SUSARs and SADRs will be reported by the Sponsor-Investigator to Swissmedic, the respective national competent authorities and the local ethical committee within 7 days in case of death; otherwise within 15 days, as well as to all investigators involved in the trial. Reports to local ethical committees will be performed by the PI of the respective site.

Any occurring adverse event will be documented and treated during and after the trial. The patients will be followed until side effects are resolved or stable for at least 3 months.

9.2.5.2 Laboratory parameters

Not applicable

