10.1.1 Definition and assessment of (serious) adverse events and other safety related events

An Adverse Event (AE) is any untoward medical occurrence in a patient or a clinical investigation participant administered a pharmaceutical product and which does not necessarily have a causal relationship with the study procedure. An AE can therefore be any unfavorable and unintended sign (including an abnormal laboratory finding), symptom, or disease temporally associated with the use of a medicinal (investigational) product, whether or not related to the medicinal (investigational) product.

A Serious Adverse Event (SAE) is classified as any untoward medical occurrence that:

- results in death.
- is life-threatening,
- requires in-patient hospitalization or prolongation of existing hospitalization.
- · results in persistent or significant disability/incapacity, or
- · is a congenital anomaly/birth defect.

In addition, important medical events that may not be immediately life-threatening or result in death, or require hospitalization, but may jeopardize the patient or may require intervention to prevent one of the other outcomes listed above should also usually be considered serious. [ICH E2A]

Examples of such events are intensive treatment in an emergency room or at home for allergic bronchospasm, blood dyscrasia or convulsions that do not result in hospitalization, or development of drug dependency or drug abuse.

SAEs should be followed until resolution or stabilization. Participants with ongoing SAEs at study termination (including safety visit) will be further followed up until recovery or until stabilization of the disease after termination.

Assessment of Causality

Both Investigator and Sponsor-investigator make a causality assessment of the event in relation to the IMP. The causality is based on the question, whether there is a "reasonable possibility" or "no reasonable possibility" that the study treatment caused the event.

Unexpected Adverse Drug Reaction

An "unexpected" adverse drug reaction is an adverse reaction, the nature or severity of which is not consistent with the applicable product information (e.g. Investigator's Brochure for drugs that are not yet approved and Product Information for approved drugs, respectively).

Suspected Unexpected Serious Adverse Reactions (SUSARs)

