10.1.2 Reporting of serious adverse events (SAE) and other safety related events

Reporting of SAEs

All SAEs must be reported immediately and within a maximum of 24 hours to the Sponsor-Investigator of the study or his substitute. The Sponsor-Investigator will re-evaluate the SAE.

SAEs resulting in death are reported to the local Ethics Committee (via local Investigator) within 7 days.

The other Ethics Committees involved in the trial as well as Swissmedic receive SAEs resulting in death via Sponsor-Investigator within 7 days.

Reporting of SUSARs

A SUSAR needs to be reported to the local Ethics Committee (local event via local Investigator) and to Swissmedic for category B and C studies (via Sponsor-Investigator) within 7 days, if the event is fatal, or within 15 days (all other events).

The Sponsor-Investigator must inform all Investigators participating in the clinical study of the occurrence of a SUSAR. All Ethics Committees involved in the trial will be informed about SUSARs in Switzerland via Sponsor-Investigator according to the same timelines.

All SAEs having a suspected link to the IMP administered (Serious adverse drug reaction (SADR)) must be reported in the same way as SUSARs.

Reporting of Safety Signals

All suspected new risks and relevant new aspects of known adverse reactions that require safety-related measures, i.e. so called safety signals, must be reported to the Sponsor-Investigator within 24 hours. The Sponsor-Investigator must report the safety signals within 7 days to the local Ethics Committee (local event via local Investigator) and to Swissmedic in case of a category B or C study.

The Sponsor-Investigator must immediately inform all participating Investigators about all safety signals. The other Ethics Committees involved in the trial will be informed about safety signals via the Sponsor-Investigator.

Reporting and Handling of Pregnancies

Pregnant participants will be followed-up in the normal way, but will not be subjected to the dGEMRIC MRI due to the need to apply a contrast agent (Dotarem®). Further follow-up after the end of the study and the outcome of the pregnancy is not necessary.

Periodic reporting of safety

A development safety update report (DSUR) is submitted once a year to the local Ethics Committees and to the national authorities via Sponsor-Investigator.

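### Protocol 3.7 exempts listed expected reactions from reporting without limiting this to non-serious events, which contradicts the protocol's SAE and SADR reporting rules

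*Protocol*

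**What the plan says.** **The exemption.** Under the heading on expected adverse reactions, Protocol 3.7 lists haematoma, bleeding and pain at the nose; pain, swelling or haematoma, and plate removal after an osteotomy at the knee; and nausea, vomiting and fever. Because these are common with standard treatment, they "therefore will only be classified according to chapter 10.1.1 and recorded in the CRF". The next sentence is "They are not subject to reporting". It does not mention seriousness and does not say to whom the report would otherwise go.

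**The reporting rules.**
- Section 9.2.5.1 refers back to the expected events of 3.7 and then states: "All SAEs will be reported to the Sponsor-investigator or his designee according to the SOP of the Sponsor".
- Section 10.1.2 begins: "All SAEs must be reported immediately and within a maximum of" 24 hours. It makes no exception for expected events.
- Section 10.1.2 also says that SAEs with a suspected link to the IMP (SADRs) "must be reported in the same way as SUSARs". Section 9.2.5.1 and the last paragraph of 2.4 likewise include SADRs in what goes to the authorities.
- The risk assessment in 3.7 itself, directly after the exemption, says: "In case of serious adverse events related to the IMP, the respective ethical commissions and national authorities will be informed".

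**Seriousness.** One SAE criterion in 10.1.1 is an event that "requires in-patient hospitalization or prolongation of existing hospitalization".

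**Safety outcome.** Sections 4.4 and 5.4 define safety by the number of SADRs and SUSARs.

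**The concern.** A site has two unqualified instructions for the same event. Post-operative pain, haematoma, fever or vomiting can plausibly lengthen a hospital stay, and 9.3.4 foresees an average stay of five days after implantation. Such an event would be on the exempt list and would also be an SAE.

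Under 10.1.1 the Sponsor-Investigator evaluates seriousness, causality and expectedness of SAEs that have been reported. An event withheld under 3.7 may therefore miss that evaluation, and the onward report to authorities and ethics committees that may follow from it. Sites could also differ in which rule they apply. Because the safety outcome is a count of SADRs and SUSARs, it matters whether that count depends on reports having been sent.

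**Working it through.** No sample size, rate or event count enters this point, so there is no figure to reproduce. The check sets the rules side by side.

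**Step 1. Can any reading of the 3.7 exemption be squared with the other rules?**

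| Reading of the exemption | 24-hour SAE rule (10.1.2) and all-SAE rule (9.2.5.1) | SADR rule (10.1.2, 9.2.5.1, end of 2.4) | Risk assessment in 3.7 |
|---|---|---|---|
| All listed events, all reporting | Conflict | Conflict | Conflict for serious IMP-related events |
| All listed events, expedited authority reporting only | No conflict | Conflict | Conflict for serious IMP-related events |
| Only listed events that meet no seriousness criterion | No conflict | No conflict | No conflict |

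The second reading has some support: 2.4 first speaks of expedited reporting for reactions that are both serious and unexpected, and leaves other events to the annual report. But 2.4 ends by including SADRs without an expectedness condition, and 10.1.2 does the same. Only the third reading is free of conflict with these rules, and 3.7 does not state it.

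**Step 2. Which safety counts could be affected?**
- *SUSARs: none.* Under 10.1.1 a SUSAR must be unexpected. A reaction whose nature or severity goes beyond the product information is unexpected by that definition, so it also lies outside an exemption for expected reactions.
- *SADRs: only if four conditions hold together.* (a) The event meets a seriousness criterion. (b) A link to the IMP is suspected. (c) The site did not report it. (d) The SADR count is compiled from SAE reports and not from the CRF.

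Condition (b) narrows the group further. Section 3.7 attributes the listed reactions mostly to tissue withdrawal and implantation, and some may be judged procedural only. Condition (d) cannot be settled: neither Protocol 5.4 and 11.4.5 nor SAP 6.1 and 6.5 names the source of the count.

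**Step 3. What stays in the record?** The listed reactions are classified under 10.1.1, which holds the SAE definition and a causality assessment by both the investigator and the Sponsor-Investigator, and they are entered in the CRF (3.7). Section 10.1 has all AEs and SAEs collected and investigated, and SAP 6.1 records them with their relationship to the IMP. One detail needs confirming: the eCRF contents in 12.1.1 name severity grade, expectedness and relationship, but not seriousness as a separate item. The form itself is not among the documents, so this does not show that the field is missing.

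**The case against.** The strongest reply is that the sentence sits in a risk-benefit narrative, while the operative chapters (9.2.5.1 and 10.1.2) agree with each other. The 3.7 risk assessment itself informs authorities of serious IMP-related events. The phrase can be read as meaning expedited authority reporting. The Sponsor's SOPs, which 10.1 says hold more detail on safety reporting, are not available and may settle the matter. Monitoring against source documents is also planned (12.3).

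Much of this limits the consequence, but it does not remove the contradiction. The expedited-reporting reading still collides with the SADR rule, and a protocol should not need an SOP to choose between two of its own instructions. What stands is that nobody can say from the documents that a site would in fact withhold a report.

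A reader might go further and infer that the exemption removes events from the safety outcome. The documents do not support that: the events are still classified and kept in the CRF, and SUSARs are outside its reach. A reader might also single out "Plate removal in case of necessary osteotomy" as the clearest serious event lost. It is a poor example. It follows an osteotomy and not the implant, the documents do not say that it needs admission, and if it counts as revision surgery, 9.2.4 assesses it whatever the cause.

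**Conclusion.** The contradiction is real and lies in the text: the exemption in 3.7 has no seriousness limit and cannot be followed together with the all-SAE and SADR rules. It is an inconsistency between stated rules and not merely missing detail.

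Its effect is a risk and not a demonstrated loss. It concerns timely reporting to, and re-evaluation by, the Sponsor-Investigator and onward reporting to authorities. It reaches the SADR count only under the four conditions above, the last of which rests on a data source that the documents do not name. No number of affected events can be derived. The point should be corrected because it touches patient safety reporting and a named outcome, and because correction is cheap.

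**What to change.** 1. Reconcile 3.7 with 2.4, 9.2.5.1, 10.1.1 and 10.1.2. State in 3.7 whether the exemption covers events that meet a seriousness criterion, and which reporting it refers to (to the Sponsor-Investigator, to authorities and ethics committees, or both), so that a serious event of a listed type follows one route. The choice of rule is the sponsor's.
2. State in the SAP that SADRs are counted from the seriousness and causality entries in the CRF, after confirming that the eCRF holds a seriousness entry.
3. Compare the CRF events of the listed types already recorded with the SAE reports received, and resolve any serious event without a report before the safety tables are produced.

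The cost is about one sentence in 3.7 with a note to sites, one sentence in the SAP, and one reconciliation listing. The SAP is dated November 2022 and already describes 24-month results, so the note to sites comes late for the main follow-up. The reconciliation is the step that can still protect the safety count.
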